## **R.2 List of Participating Investigational Centers**

The list of participating Investigational Centers will be provided under separate cover.

#### **R.4 Additional Records and Reports**

No additional records and/or reports, other than those previously described in this investigational plan or required by FDA, will be maintained for this clinical investigation.

## **R.5 Sample Case Report Forms**

Sample Case Report Forms (CRFs) will be provided under separate cover.

## R.6 Aortogram Acquisition Guidelines

The purpose of the acquisition guidelines is to increase consistency and effectiveness in reviewing the procedural aortograms.

### 1. Required aortogram:

- Index Procedure –TAVI

### 2. Required cine runs:

- Pre-procedure aortogram in a projection with 3 aortic cusps aligned (for comparison of final aortogram with pre-procedure aortogram)
- Final aortogram at least 10 minutes after TAVI implantation in the exact same projection as the pre-procedure aortogram (in order to measure depth of implantation and assess grade of aortic regurgitation)

**NOTE:** If the apex is not clearly visible in the final projection and in case of adequate renal function, in order to assess grade of AR, perform an additional final aortogram in RAO 30° with visualization of the left ventricle in long axis, including the apex.

### 3. Guidelines on how final aortogram after deployment of the valve should be performed:

- Use at least 20 ml of contrast, with an injection rate of 20 ml/sec
- Position the pigtail catheter in the upper third part of the frame
- Preferably use non-diluted contrast. 50%-diluted contrast is acceptable in case of renal insufficiency
- Use the angiographic projection with the three aortic cusps aligned in 1 plane:
  - Whenever available this optimal projection can be suggested by baseline MSCT exam
  - Pragmatic approach might be to use a shallow LAO or RAO projection, and adjust in a cranial or caudal position respectively to approach the optimal projection
- Confirm visualization of the left ventricular apex on the final aortogram
- Perform the final aortogram at least 10 minutes after deployment of the investigational TAVI device; include a time indication on the aortogram
- Use marker pigtail or provide the French-size of the pigtail catheter for calibration purpose

[figure not shown]
### 4. General imaging and recording procedures:

- Use a fixed table system and biplane x-ray equipment, if available
- Recommended resolution: 1024 x 1024 pixels
- Preferred acquisition speed: 25 frames/second
- One single cine run should have a duration of at least 5 heart beats
- The digital clock should be activated
- The maximum magnification factor should be applied during cine run without losing the image of the entire frame
- There should be no overlap of the frame with other catheters or electrodes
- Foreshortening of the frame should be avoided as much as possible
- Upload all images to InteleGRID (secure electronic system used for transferring images)

**5. Core lab analysis:**

The procedural aortograms may be analyzed by a core laboratory. Analysis would include:

- Grade of aortic regurgitation
- Depth of implantation

**Figure 1:** Example of depth of implantation measurement.

## R.7 Echocardiography Acquisition Guidelines

### 1. Scope of the document

These guidelines aim to increase consistency and effectiveness in collection and adjudication of echocardiography data of selected candidates for the SURTAVI trial. Optimal image acquisition, storage, and transmission will be described.

### 2. Protocol required echocardiograms

Transthoracic echocardiography is required at the following intervals:

Screening	- 45 days of Heart Team review
Post-Procedure OR Discharge	Between 24hrs post-procedure and hospital discharge (but no later than 7 days from post Index Procedure)
6 months	± 30 days
12 months	± 30 days
24 months	± 60 days
3,4,5 years	± 60 days

### 3. Four general rules for echocardiography recordings

3.1 Rule #1 for overall recordings: adhere STRICTLY to the PROTOCOL regarding:

- **number** and **order** of recordings as listed on the Table
- **do not perform measurements** on the echo recordings, except screening echo to be submitted for screening committee review (see measurements noted in section 4)
- at end of echo exam, export all required recordings in **DICOM** format and upload it to InteGRID
- only one **certified** echocardiographer (+ 1 replacement) is allowed to participate in the study, he/she should print his/her name, fill in contact details and sign the transmittal form

3.2 Rule #2 for Doppler recordings:

- Unless stated otherwise, all pulsed-wave and continuous-wave Doppler signals should be recorded at a **sweep speed of 50-100 mm/sec** (recording must contain minimum of three heartbeats) with optimized gain and filter setting, baseline position, and velocity range.

3.3 Rule #3 for apical 2D views (4-, 5-, 2-, and 3-Chamber views)

- pay attention to ultrasound sector **depth** and **gain** settings
- the aortic valve should be out of scan plane in the 4-CH view
- please avoid patient or transducer **motion** and record during **quite respiration** unless stated otherwise
- make sure the **entire LV myocardium** (including epicardium and apex) is recorded in the scan sector in particular at end-diastole
- make sure **Frame Rate** is more than 30Hz for 2D grey-scale and around 20Hz for colour Doppler aortic regurgitation

3.4 Rule #4 for EF calculation (apical 4-, 2-, and 3-Chamber views focused on LV)

- Record **3 runs** (run 1: 3 beats, run 2: 3 beats, run 3: 10 beats)

### 4. Data requirements

Participating centers in the SURTAVI study should obtain the appropriate Doppler and echocardiography recordings to document the following variables.

- Aortic annulus long-axis diameter in mid-systole (screening/baseline only)\*
- LVOT long axis diameter in mid-systole
- Sinus of Valsalva diameter (SOV) at end diastole (screening/baseline only)\*
- Sino-tubular junction diameter (STJ) at end diastole (screening/baseline only)\*
- Sinus of Valsalva height (SOVH) at end-diastole (screening/baseline only)\*
- Max aortic valve velocity (V2) by CW Doppler
- Velocity time integral (VTI) across aortic valve by CW Doppler
- Mean gradient across aortic valve (MGV2) by CW Doppler\*
- Peak LVOT velocity (V1) by PW Doppler
- Velocity Ratio (V1 / V2)
- Velocity time integral (VTI) of LVOT velocity by PW Doppler
- Mean LVOT gradient (MGV1) by PW Doppler
- Doppler Velocity Index (DVI) =  $VTI_{LVOT} / VTI_{Ao}$
- Grade of aortic transvalvular regurgitation
- Grade of aortic paravalvular regurgitation
- Grade of mitral regurgitation
- PISA for MR (optional)
- Max tricuspid regurgitant (TR) jet velocity (if TR is present)
- Left ventricular (LV) end-diastolic diameter (LVEDD)
- Left ventricular (LV) end-systolic diameter (LVESD)
- Interventricular septal thickness at end diastole
- Left ventricular posterior wall thickness at end diastole
- Left atrial diameter (AP linear dimension) at end systole
- Left ventricular ejection fraction by visual estimate
- Heart rate from Doppler signal
- Mitral inflow "A" velocity
- Mitral inflow "E" velocity
- Mitral inflow E-wave deceleration time
- Mitral annular tissue Doppler systolic velocity (septal and lateral)
- Mitral annular tissue Doppler early diastolic velocity (septal and lateral)
- Mitral annular tissue Doppler late diastolic velocity (septal and lateral)

Procedures for acquiring aortic root measurements and key hemodynamic variables are described in the following sections. For Doppler velocities, the values reported should represent the average of measurements from at least three cardiac cycles for patients in sinus rhythm, and the average of measurements from five cardiac cycles for patients not in sinus rhythm. For aortic valve, TR jet, and tissue Doppler velocities, the reported values should represent the average of the highest velocities obtained from the same transducer position.

\* Screening/baseline measurements should be noted on the echo submitted for Screening Committee review.

**5. Table 1. list of echo recordings (views)**

- Please include all LV walls including epicardium are within the scan sector
- Please enter patient's height, weight, and blood pressure during echo acquisition
- Please optimize frame rate of 2D colour Doppler around 20 Hz if possible
- Shift the colour flow zero baseline downwards or upwards in the regurgitant jet direction in the left PLAX view depending on the jet orientation and upwards in the apical view
- Record frozen images & cine loops in the following order:

**A: From parasternal long-axis window**

1. 2D greyscale standard view
2. 2D Colour Doppler of mitral regurgitation (MR)
3. 2D Colour Doppler of aortic (or prosthetic) regurgitation (AR)
4. If AR is present, **ZOOM** & narrow sector with focus on vena contracta of regurgitant jet
5. If AR is present, **ZOOM** & narrow sector, shift Nyquist 35-40 for PISA measurements
6. 2D greyscale **ZOOM** for LV outflow tract diameter (LVOT) (**3 recordings**)
7. 2D greyscale **ZOOM** at an intercostal space higher for aortic root / aortic prosthesis

**B: From parasternal short-axis window (use same depth setting)**

8. 2D greyscale LV at mitral valve level
9. 2D greyscale LV at papillary muscle level
10. 2D greyscale-guided M-mode at LV minor axis (LV dimensions, avoid papillary muscles)
11. 2D greyscale LV at apical level: *lower your transducer position by 1 or 2 intercostal spaces and record the LV as circular as possible, just proximal to the level with end-systolic LV luminal obliteration*
12. 2D greyscale aortic valve level (post TAVI the native annulus is usually identified by maximal calcification)
13. 2D greyscale-guided M-mode of left atrial & aortic dimensions
14. 2D Colour Doppler of AR: *in post-TAVI start scanning from highest position and record first visible AR jet, scan more downwards and try to pick up additional jets – confirm origin of AR jets from PLAX*
15. 2D greyscale **ZOOM** & focussed on RV outflow tract (RVOT) – pulmonic valve should be visible
16. 2D Colour Doppler of pulmonary regurgitation (PR)
17. If PR is present, CWD of PR jet (include both systolic & diastolic signals)
18. PWD of RVOT velocity (within 0.5 -1cm below the pulmonic valve) (frozen image)

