**Note: Velocity tracings should be noted on images submitted for Screening Committee review**

**Note: Fine linear signals at peak velocity should not be included in the velocity tracings!**

## 12. Assessment of Aortic Regurgitation

- **Use all echo modalities:** An integrated exam approach using colour flow, pulsed-wave (PW), and continuous-wave (CW) Doppler is used to assess the severity of transvalvular and paravalvular regurgitation.
- **Use four views:** Colour flow Doppler imaging should be performed from the parasternal long and short-axis views, and the apical long-axis and apical 5-chamber views. A recording of the aortic regurgitant signal should be obtained with CW Doppler. If the degree of aortic regurgitation appears more than mild by visual estimate, the velocity in the proximal descending aorta and the abdominal aorta should be recorded with PW Doppler.
- **Severity:** The degree of transvalvular and paravalvular AR will be graded as none, trace, mild, moderate, and severe based on the analysis of the parameters shown in Table 2a.
  - The category of “trace” is used in cases where regurgitation is barely detectable by colour Doppler.
  - Regurgitant signals observed to originate within the stent will be considered transvalvular, and regurgitant signals observed to originate outside the stent will be considered paravalvular.
- Paravalvular regurgitant jets will be characterized by the extent of the aortic regurgitant jet relative to the short axis circumference of the aortic valve (Table 2a- Valve Academic Research Consortium (VARC) Consensus Report for Transcatheter Aortic Valve Implantation (TAVI) and Table 2b. Updated standardized endpoint definitions for transcatheter aortic valve implantation: the VARC-2 consensus document, and Table 3a and b -2008 Focused Update Incorporated Into the ACC/AHA 2006 Guidelines for the Management of Patients With Valvular Heart Disease (published in the October 2008 issues of Journal of the American College of Cardiology and Circulation).

**Table 2a.** Parameters for evaluation of the severity of aortic regurgitation

Prosthetic Aortic Valve Regurgitation Criteria (Central and Paravalvular)			
Parameter	Mild	Moderate	Severe
Valve Structure and Motion Mechanical or bioprosthesis	Usually normal	Usually abnormal†	Usually abnormal†

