Structural parameters Left ventricular size	Normal ‡	Normal/ mildly dilated ‡	Dilated
Doppler parameters (qualitative or semi quantitative) Jet width in central jets (% LVO diameter): colour* Jet density: CW Doppler Jet deceleration rate (PHT † , ms): CW Doppler** LV outflow vs. pulmonary flow: PW Doppler Diastolic: flow reversal in the descending aorta PW Doppler  Circumferential extent of paraprosthetic AR (%)	Narrow (≤25%) Incomplete or faint  Slow (>500) Slightly increased  Absent or brief early diastolic  <10	Intermediate (26-64%) Dense  Variable (200-500) Intermediate  Intermediate  10-20	Large (≥65%) Dense  Steep (<200) Greatly Increased  Prominent, Holodiastolic  >20
Doppler parameters (quantitative) Regurgitant volume (mL/beat) Regurgitant fraction (%)	<30 <30	30-59 30-50	>60 >50

\* Parameter applicable to central jets and is less accurate in eccentric jets

\*\* Influenced by left ventricular compliance

AR=aortic regurgitation; CW= continuous wave; LVO= left ventricular outflow; PW= pulsed wave

† PHT is shortened with increasing LV diastolic pressure and vasodilator therapy, and may be lengthened in chronic adaptation to severe aortic regurgitation. As such, PH, in contrast to the other parameters, does not reflect the volumetric severity of aortic regurgitation, but rather its hemodynamic impact. Therefore, in the setting of acute paravalvular or transvalvular leaks, intermediate values between 200 and 500 ms should not be used to classify the degree of regurgitation.

‡ Abnormal mechanical valves, for example, immobile occluder (valvular regurgitation), dehiscence or rocking (paravalvular regurgitation); abnormal biologic valves, for example, leaflet thickening or prolapse (valvular), dehiscence or rocking (paravalvular regurgitation).

‡ Applies to chronic, late postoperative AR in the absence of other etiologies.

**Table 2b.** VARC-2 criteria for evaluation of the prosthetic valve dysfunction

Prosthetic valve dysfunction			
Prosthetic aortic valve stenosis*			
	Normal	Mild Stenosis	Moderate/Severe Stenosis
Quantitative Parameters (Flow-dependent)†			
Peak velocity	<3 m/s	3-4 m/s	>4 m/s
Mean gradient	<20 mmHg	20-40 mmHg	>40 mmHg
Quantitative Parameters (Flow-independent)			
Doppler velocity index‡	>0.35	0.35-0.25	<0.25
Effective orifice area¶	>1.1 cm 	1.1-0.8 cm 	<0.8 cm 

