where  $\pi_{TAVI}$  and  $\pi_{SAVR}$  denote the binary rate of all strokes at 30 days or hospital discharge (if longer). The posterior probability  $P(H | \text{data})$  will be calculated and compared to a threshold of 0.975. The statistical method will be the Bayesian version of a comparison of proportions (see Section C.11).

17. Incidence of moderate/severe aortic insufficiency after TAVI vs. SAVR (secondary objective #12). The hypothesis of interest is

$$H: \pi_{TAVI} < \pi_{SAVR}$$

where  $\pi_{TAVI}$  and  $\pi_{SAVR}$  denote the proportion of subjects with moderate/severe aortic insufficiency at the discharge echo. The posterior probability  $P(H | \text{data})$  will be calculated and compared to a threshold of 0.975. The statistical method will be the Bayesian version of a comparison of proportions (see Section C.11).

18. New pacemaker implant rate for TAVI at 30 days or hospital discharge, whichever is longer (secondary objective #7). The hypothesis of interest is

$$H: \pi_{TAVI} < 30\%$$

where  $\pi_{TAVI}$  denote the binary rate of new pacemaker implants for TAVI at 30 days or hospital discharge (if longer). The posterior probability  $P(H | \text{data})$  will be calculated and compared to a threshold of 0.975. The statistical method will be the Bayesian version of a comparison of proportions (see Section C.11).

Other than the hierarchical testing procedure described above, no further multiplicity adjustments will be made in the analyses of the secondary endpoints. Summary data from other secondary objectives, such as device success and procedural success from secondary objectives #20 and #21, respectively, may be provided in the device labeling. However, no claims of statistical significance or other statistical inference will be made.

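### The echo guideline prescribes an active short-axis sweep for further regurgitant jets only after TAVI, so the TAVI-versus-SAVR regurgitation comparison is open to detection bias against TAVI

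*Combined protocol and SAP*

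**What the plan says.** R.7 section 5, Table 1, lists the recordings for every study echo. Part B, item 14 is short-axis colour Doppler of AR. Its added instruction applies to one device: "in post-TAVI start scanning from highest position and record first visible AR jet, scan more downwards and try to pick up additional jets". The same item then tells the sonographer to "confirm origin of AR jets from PLAX". Section 3.1 requires sites to "adhere STRICTLY to the PROTOCOL regarding" the number and order of the listed recordings.

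Most of the remaining AR work-up is common to both arms. The long-axis colour item covers native and prosthetic valves alike. Section 12 states: "Colour flow Doppler imaging should be performed from the parasternal long and short-axis views, and the apical long-axis and apical 5-chamber views". It also states: "An integrated exam approach using colour flow, pulsed-wave (PW), and continuous-wave (CW) Doppler is used to assess the severity". Section 12 characterises paravalvular jets by their extent around the short-axis circumference, and Table 2a grades "Circumferential extent of paraprosthetic AR" among its parameters. Section 18 makes Echo Core Lab data primary.

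In the current SAP (based on CIP Version 12.0), AR is compared between arms in secondary endpoint 12 (C.10). It also enters Major Adverse Events, Clinical Efficacy and Time-Related Safety. In objective 17 (C.12.1), a TAVI superiority test at a posterior threshold of 0.975, the two rates "denote the proportion of subjects with moderate/severe aortic insufficiency at the discharge echo".

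**The concern.** A between-arm comparison of a detected finding needs equal detection effort. Here the text requires the sonographer to look for more than one jet in the TAVI arm and leaves this to local habit in the SAVR arm. The difference falls in the view where circumferential extent is read. A core lab common to both arms cannot correct it, because it can grade only what was recorded.

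If the sweep finds jets that would otherwise be missed, and some of them move a grade to moderate or severe, part of the observed TAVI-minus-SAVR difference comes from acquisition. That would affect the safety description of the device, three composites and a labeling objective. Failing objective 17 would also stop the sequence before objective 18, the pacemaker rate.

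**Working it through.** **Figures in the plan.** The documents give no AR rate, no power for objective 17 and no detection sensitivity. There is no stated figure to reproduce, so the point rests on the wording.

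**Step 1: compare the arms.**

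| Element of the AR work-up | TAVI | SAVR |
|---|---|---|
| Short-axis colour recording (item 14) | Yes | Yes |
| Top-to-bottom sweep for further jets | Prescribed | Not prescribed |
| Long-axis confirmation of jet origin attached to the sweep | Prescribed | Not prescribed |
| Four colour views (section 12) | Yes | Yes |
| Integrated colour, PW and CW grading (section 12) | Yes | Yes |
| Echo Core Lab data primary (section 18) | Yes | Yes |

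The arms differ only in the sweep and its attached check.

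**Step 2: can a missed jet change a grade?** Mild is below 10% of the circumference in Tables 2a and 2b; moderate is 10-20% in Table 2a and 10-29% in Table 2b. Suppose there are two jets of 7% each. If one were missed, the extent would read 7% (mild). With both recorded it is 7 + 7 = 14% (moderate in either table). A change is therefore possible on this parameter. It is not automatic, because extent is one of several parameters and no text limits a SAVR exam to one jet.

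**Step 3: illustration of the effect on objective 17.** Inputs from the plan: 1600 mITT subjects randomised 1:1 (C.4.2), so about 800 per arm, and the 0.975 threshold, taken as one-sided 0.025. Assumed: true moderate/severe rates p_T and p_S, TAVI cases all detected, SAVR cases detected with relative probability s.

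- Observed rates: a = p_T and b = s × p_S
- SE = √{[a(1−a) + b(1−b)] / 800}
- P(TAVI declared superior) = Φ((b−a)/SE − 1.96)
- P(SAVR looks better) = Φ((a−b)/SE − 1.96)

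Example with p_T = p_S = 0.05 and s = 0.9: a = 0.050 and b = 0.045. SE = √[(0.0475 + 0.042975)/800] = 0.01063, and (a−b)/SE = 0.470. P(TAVI superior) = Φ(−2.430) = 0.0075. P(SAVR looks better) = Φ(−1.490) = 0.068.

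Equal true rates:

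| True rate, both arms | s | Apparent TAVI excess | P(TAVI superior) | P(SAVR looks better) |
|---|---|---|---|---|
| any | 1 | 0 | 0.025 | 0.025 |
| 2% | 0.9 | 0.2 points | 0.012 | 0.048 |
| 2% | 0.8 | 0.4 points | 0.005 | 0.087 |
| 5% | 0.98 | 0.1 points | 0.020 | 0.031 |
| 5% | 0.9 | 0.5 points | 0.008 | 0.068 |
| 5% | 0.8 | 1.0 points | 0.002 | 0.160 |
| 8% | 0.9 | 0.8 points | 0.005 | 0.088 |
| 8% | 0.8 | 1.6 points | 0.001 | 0.235 |

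For a true TAVI advantage, say 2% against 4%, the same formula gives P(TAVI superior) of 0.65 at s = 1, 0.62 at s = 0.98, 0.49 at s = 0.9 and 0.33 at s = 0.8. If the true rates are reversed (4% TAVI, 2% SAVR), objective 17 essentially never passes at any of these values of s.

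The direction is the same throughout: against TAVI. The size depends entirely on s and the true rates, which have no source in the documents.

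**The case against.** The strongest reply is that not prescribing a SAVR sweep is not evidence that SAVR exams miss jets. Item 14 concerns one view of four, and the other views, the grading approach and the core lab are common to both arms. A Table 2b footnote warns that circumferential extent is poorly validated and may overstate severity. The strict-adherence rule governs the number and order of recordings and does not forbid sweeping a surgical valve. All of this stands. A reader might infer that the AR comparison *is* biased, but the documents do not support that; they show only unequal prescribed effort.

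A second reply is that the direction protects against a false claim. This also stands: lower SAVR detection cannot produce a false TAVI superiority finding. Objective 17 is also reached only after primary non-inferiority, the four secondary non-inferiority tests and superiority objectives 5-16 have passed. A reader might treat the pass probabilities above as the loss of a labeling claim. They are conditional on reaching objective 17 and on unsourced inputs.

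Third, the sweep may reflect a frame that spans several levels; other R.7 items are device-specific too. That is plausible, but the text gives no such reason for item 14, and it would not make the same sweep unsuitable after surgery.

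Fourth, the edit comes late. The SAP revision history puts accrual at approximately 1600 mITT subjects when the margin changed, so nearly all discharge echoes already exist. A change now would also make later SAVR echoes differ in method from earlier ones. This stands, and it is why a caveat is needed as well as the edit.

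**Conclusion.** The point holds as a risk of detection bias that the text itself creates. Prescribed search effort differs by randomised arm in the view used for paravalvular extent, while AR is compared between arms in secondary endpoint 12, objective 17 and three composites. Any effect runs against TAVI. It is conservative for objective 17, but it could exaggerate a TAVI leak excess or hide a TAVI advantage.

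Its size cannot be established. Under the assumptions shown it ranges from negligible (s = 0.98) to an apparent excess of 1.6 percentage points (8% true rate, s = 0.8). It matters only if the added jets move grades to moderate or severe.

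The check covers the CIP appendices and the SAPs. The main body of the CIP was not available for it, so a surgical-valve echo instruction there would narrow or remove the point.

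**What to change.** In R.7 Table 1 item 14, replace the restriction to TAVI exams with wording that covers any aortic prosthesis, TAVI or SAVR. The same short-axis sweep, recording of all jets and long-axis confirmation then apply in both arms at every post-procedure echo. If the sponsor regards the sweep as device-specific, R.7 should say why.

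For echoes already acquired under the present wording, report endpoint 12, objective 17 and the AR-containing composites with a stated caveat that acquisition differed by arm and that the likely direction is against TAVI. Record the date on which the new wording took effect, so that a change in SAVR detection over time can be recognised.

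The cost is one phrase in the echo appendix, a few seconds of scanning per SAVR exam and a sentence in the report. No visit, staff or equipment is added. The edit cannot repair existing discharge echoes.
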